Study Duration	48 months
Subject Participation Duration	Estimated length of participation by each individual: 4-6 months Estimated study accrual time: 40 months
Single or Multi-Site	Single-site
Objectives	To investigate the effect of intra-muscular BTX-A injections on pain and physical well-being during the expansion period in women undergoing unilateral and bilateral mastectomies with immediate placement of subpectoral tissue expanders.
Number of Subjects	134
Diagnosis and Main Inclusion Criteria	Women at least 18 years of age, who will undergo immediate unilateral or bilateral tissue expander breast reconstruction.
Study Product, Dose, Route, Regimen	Botulinum Toxin A (BOTOX-A®, Allergan Inc.) Single dose of 100 units of BTX-A injected intra-operatively in the pectoralis major muscle. Maximum dose per patient is 100 units of BTX-A for unilateral tissue expander placement, and 200 units for bilateral tissue expander placement.
Duration of Administration	Single intra-operative dose
Reference therapy	Placebo control group (intra-operative saline injection)
Statistical Methodology	Outcome variables will be summarized overall and by treatment group with frequency counts and percentages or means, standard deviations, medians, and ranges, as appropriate. Variables will be compared by treatment group using two-sample t, Wilcoxon rank sum, Pearson's chi-square, or Fisher's exact tests.

Abstract

As part of an ongoing effort to improve quality of patient care in plastic surgery, we propose to investigate the effect of intra-muscular Botulinum toxin A (BTX-A) injections on pain and physical well-being in women undergoing mastectomies with immediate placement of tissue expanders. Implant-based breast reconstruction is frequently achieved in two-stages. The first stage consists of the placement of a tissue expander after mastectomy. This is followed by a period of tissue expansion lasting several months. In the second stage, the tissue expander is replaced with a permanent breast implant. Despite the well-recognized advantages of this successful technique, the subpectoral placement of a tissue expander is associated with significant pain and discomfort in the immediate post-operative period and during the phase of tissue expansion.¹⁻¹¹ Although the potential for a therapeutic use of BTX-A as an analgesic agent is well established in various clinical problems¹²⁻²³, there is a paucity of data assessing the effects of BTX-A in relieving pain associated with tissue expander breast reconstruction. We performed a systematic review of the literature, to identify existing data on the use of BTX-A with subpectoral tissue expanders.²⁴ The largest study of the effect of BTX-A on pain during tissue expansion was published by Layeeque et al.²⁵ In this retrospective study, the authors reported a significant reduction in pain postoperatively and during tissue expansion with the use of BTX-A. Since 2008, BTX-A has been routinely used at Mayo Clinic to alleviate pain associated with tissue expansion. A preliminary analysis of our pilot data confirms the findings previously reported by Layeeque et al. We propose to conduct a multi-center, double-blinded prospective randomized controlled trial (PRCT) of women undergoing unilateral and bilateral mastectomies with immediate placement of tissue expanders, to establish the efficacy of BTX-A on alleviating pain and on improving physical well-being during the expansion period.

1 Introduction

This document is a protocol for a human research study. This study will be carried out in accordance with the applicable United States government regulations and Institutional research policies and procedures.

HUMAN SUBJECTS

Institutional Review Board (IRB) approval will be obtained to conduct this study. Although no identifiable Protected Health Information (PHI) will be transmitted to the study's database, study staff will comply with HIPAA guidelines for the protection of PHI. All data gathered will be de-identified and kept in a secured location. Medical records will be assigned code numbers, so that names will not be connected to any information. The following safeguards will be used with respect to protection of human subjects:

Recruitment and Informed Consent: Eligible women will be invited to participate in the study by a member of the patient's surgeon/treatment team or the study's research coordinator at Mayo Clinic, at the time of their preoperative assessment by a plastic surgeon. Electronic medical records will be examined to confirm subjects' eligibility for study participation. Women who agree to participate will receive documents describing the purpose and details of the study, information about confidentiality and sharing of information within the research team, as well as an informed consent form. They will have a full opportunity to ask questions about the study and may decide at any point to decline participation in the study. Should patients have additional questions about the study, contact information for a project research coordinator will be provided in the informational documentation. If eligible women do not wish to participate in the study, no further effort will be made to contact them.

Confidentiality Safeguards: Participants will be notified that information collected during their participation in this study is considered confidential. All data gathered in the study will be de-identified and kept in a password-protected study-specific database at Mayo Clinic. Confidentiality of each participant's data will be protected with all data identified solely by a code number. Names will not be connected to any information. Only the authors of the study will have access to this information, and patient details will be filed under code number, not under patient name. A list matching subject names and code numbers will be maintained on a separate sheet of paper kept in locked storage; only the authors of the study will have access to this information. This information will be kept on a computer in a locked departmental office at all times. Information from any woman who is enrolled but later determined to be ineligible will be retained in a confidential electronic data base.

Sources of Materials: Participants' responses to the NPIS and the BREAST-Q® will be the main source of research material. Patient information will also be obtained from existing electronic medical records. These data will be collected for research purposes only and not used for any other purposes.

Data Safety and Monitoring Plan (DSMP): A Data Safety and Monitoring Plan (DSMP) will allow us to identify adverse events and accrual problems. A statistician will review the unblinded adverse event data after 1/2 of the target sample size has accumulated.

Data Safety and Monitoring Board (DSMB): An independent Data Safety and Monitoring Board will consist of [name], [name], [name], [name], [name], [name] and a Mayo Clinic statistician who is not involved with this project. The Data Safety Monitoring Board will assess safety and efficacy at interim analysis (when 75 patients have been enrolled) and whenever necessary.

Median Lethal Dose:

The median lethal dose is estimated to be approximately 39 units of BTX-A per kilogram of body weight.²⁶

Safety, Risks and Adverse Effects:

BTX-A has been used as a therapeutic agent since the late 1970s. Since then, it has been demonstrated to be a remarkably safe drug when used under medical supervision.^{27, 28} The mechanism of action of BTX-A has been extensively studied and is known to be very specific. Thus, non-neuromuscular adverse effects and systemic side effects are very rare.²⁹ Local side effects of BTX-A injection include a flu-like syndrome that is generally short-lived, dysphagia, and xerostomia. Unintended weakness of the muscle injected or of nearby muscles could also be a negative effect. Other potential side effects include muscle soreness, rash, headaches, light-headedness, fever, chills, hypertension, diarrhea and abdominal pain.

1.1 Background

Significance: Each year, the number of breast cancer survivors who choose post-mastectomy breast reconstruction keeps rising. Among women who elect to pursue breast reconstruction, approximately 75% will choose prosthetic breast reconstruction.³⁰ By far, the most commonly employed surgical technique utilizes tissue expanders as a first stage. Tissue expansion is a well-established breast reconstruction technique characterized by high success rates and high patient satisfaction.^{9, 31-36} However, women report significant amounts of pain and discomfort with this technique.^{1, 8, 11, 37} Legeby et al. recently showed that women who underwent prosthetic breast reconstruction had higher pain scores and took more analgesics than those who did not choose post-mastectomy reconstruction.⁸

In the past 10 years, publications on the use of BTX-A for pain relief in a wide array of clinical conditions have increased tremendously. BTX-A is one of the neurotoxins produced by Clostridium botulinum bacteria. By reversibly inhibiting neurotransmitter release, BTX-A has both analgesic³⁸ and paralytic properties.²⁸ The presence of analgesic properties of BTX-A is increasingly supported by several clinical observations: pain relief with BTX-A injections has been reported for migraine headaches³⁹, chronic pelvic pain^{15, 20, 40, 41}, chronic tennis elbow²¹, and post-operative pain control for lower limb lengthening correction^{16, 42}, among others.

Reduced pain and improved physical well-being are felt to contribute to an enhanced QoL for women who elect to pursue breast reconstruction. Moreover, clinically meaningful benefits of BTX-A on physical well-being and overall QoL of patients treated with this biologic agent have recently been highlighted in a systematic review.⁴³ Our contribution here is expected to provide high-level evidence of the efficacy of BTX-A on pain and physical well-being during the expansion phase of two-stage

breast reconstruction. In the current environment of rising healthcare costs and increased government scrutiny on marketing for off-label indications of BTX-A⁴⁴, this study can provide exactly the type of data needed by the United States Food and Drug Administration (FDA) to expand approved uses of products and devices.

Background: Although there are presently nine FDA approved indications for the clinical use of BTX-A (1- Cervical dystonia, 2- Severe primary axillary hyperhidrosis, 3- Strabismus, 4- Blepharospasm, 5- Temporary improvement in the appearance of moderate to severe glabellar lines, 6- Chronic migraine, 7- Upper limb spasticity, 8- overactive bladder symptoms, 9- Crow's feet), off-label use of BTX-A has rapidly expanded beyond these approved clinical indications. One of the most rapidly expanding indications for BTX-A is in the treatment of various painful muscle spasms (e.g. paravertebral muscle spasm⁴⁵, fibromyalgia-myofascial pain⁴⁶, temporomandibular joint pain⁴⁷, etc.). Pectoralis major muscle spasm is a frequently reported problem during tissue expansion. The neuromuscular and analgesic effects of BTX-A have been studied in a wide spectrum of spastic disorders, namely for the treatment of spasticity associated with disorders such as stroke¹⁹, multiple sclerosis, Parkinson's disease and cerebral palsy. Recently, emerging evidence has been published on the use of BTX-A for the treatment of migraine headaches^{14, 39} and musculoskeletal disorders.⁴⁸ To the best of our knowledge, this aspect has never been studied in breast cancer survivors who elect to pursue breast reconstruction with tissue expanders. Furthermore, physical function outcomes are important to consider with BTX-A use because the link between temporary muscle paralysis and improvements in participation in daily activities is not a given.

Pain is the most commonly reported complication associated with the use of tissue expanders, and yet suboptimal pain control with the use of oral narcotics remains the current standard of care. Over the years, numerous methods to decrease pain associated with the process of tissue expansion have been tested and yielded unsatisfactory results.^{2-5, 10, 49} For example, Sinow et al. experimented with intraluminal injections of lidocaine in tissue expanders, but were unable to demonstrate any reduction in pain when lidocaine was compared with placebo.² Moreover, in recent years, innovation in prosthetic breast reconstruction techniques has seen a rapid rise in popularity of acellular dermal matrix (ADM).⁵⁰⁻⁵³ Many plastic surgeons have incorporated ADM in their surgical practice for one-stage and two-stage prosthetic breast reconstruction.⁵⁴⁻⁵⁶ ADM is frequently used as a sling to cover the lower lateral pole of tissue expanders and implants in breast reconstruction.⁵⁷ Potential benefits may include: 1) improved control of the submuscular pocket and infra-mammary fold;^{57, 58} 2) higher initial filling volumes of tissue expanders at the time of placement; 3) reduced overall number of expansions; and 4) decreased pain morbidity associated with the musculofascial dissection (rectus abdominus and serratus anterior). At the present time, possible benefits of ADM on postoperative pain alleviation have not been demonstrated in prospective clinical trials. The research proposed in this application is innovative, in our opinion, because it represents a new and substantive departure from the status quo in pain management following tissue expander breast reconstruction. An additional strength of this investigation is that it will include a newly developed patient-reported outcome (PRO) measure to study physical well-being. The BREAST-Q® was rigorously developed and validated with adherence to guidelines set by the Medical Outcomes Trust⁵⁹ and the FDA.⁶⁰

1.2 Investigational Agent

Commercially available in the United States under the brand name BOTOX®, FDA approved BTX-A will be used as the investigational agent against a placebo. BTX-A will be obtained from the manufacturer, Allergan Inc. (Irvine, CA), and dispensed through the institutional research pharmacy.

BOTOX®, onabotulinumtoxin A or botulinum toxin type A, is one of the neurotoxins produced by the Gram positive, anaerobic *Clostridium botulinum* bacteria that causes botulism. It blocks neuromuscular transmission by binding to acceptor sites on motor or sympathetic nerve terminals, entering the nerve terminals, and inhibiting the release of acetylcholine. This inhibition occurs as the neurotoxin cleaves SNAP-25, a protein integral to the successful docking and release of acetylcholine from vesicles situated within nerve endings. When injected intramuscularly at therapeutic doses, BTX-A produces partial chemical denervation of the muscle resulting in a localized reduction in muscle activity. In addition, the muscle may atrophy, axonal sprouting may occur, and extrajunctional acetylcholine receptors may develop. There is evidence that reinnervation of the muscle may occur, thus slowly reversing muscle denervation produced by BTX-A. Using currently available analytical technology, it is not possible to detect BTX-A in the peripheral blood following intramuscular injection at the recommended doses.

BOTOX® for injection is a sterile, vacuum-dried purified botulinum toxin type A, produced from fermentation of a strain *Clostridium botulinum* type A, and intended for intramuscular and intradermal use. It is purified from the culture solution by dialysis and a series of acid precipitations to a complex consisting of the neurotoxin, and several accessory proteins. The complex is dissolved in sterile sodium chloride solution containing Albumin Human and is sterile filtered (0.2 microns) prior to filling and vacuum-drying. One Unit of BTX-A corresponds to the calculated median intraperitoneal lethal dose (LD₅₀) in mice. Each vial of BOTOX® contains either 100 Units of *Clostridium botulinum* type A neurotoxin complex, 0.5 mg of Albumin Human, and 0.9 mg of sodium chloride; or 200 Units of *Clostridium botulinum* type A neurotoxin complex, 1 mg of Albumin Human, and 1.8 mg of sodium chloride in a sterile, vacuum-dried form without a preservative.

1.3 Pre clinical data or other off label use

This is an FDA approved product in commercial distribution. Detailed information on specific warnings, precautions, contraindications and adverse reaction is available from the Package Insert. (See Attached)

In the late 1970s, the first therapeutic use of BTX-A was as a treatment for strabismus.^{61, 62} By reversibly inhibiting neurotransmitter release, BTX-A has both analgesic and paralytic properties. When injected intramuscularly at therapeutic doses, BTX-A produces chemical denervation of the muscle, thus resulting in localized muscle weakness. This effect occurs within a few days to one week after injection, peaks within two weeks and lasts several weeks, before hitting a plateau and then gradually returning to baseline levels of muscle contraction.²⁸ The clinical effects last three to four months after each injection.²⁸ The analgesic action of BTX-A was initially thought to be related to its effects on muscular contraction. However, a recent in vitro study of embryonic rat dorsal neurons did

confirm that BTX-A inhibits release of substance P, a neurotransmitter associated with pain and inflammatory reactions.³⁸ Moreover, this analgesic property of BTX-A is increasingly supported by several clinical observations: pain relief with BTX-A injections has been reported for migraine headaches³⁹, chronic pelvic pain^{15, 20, 40, 41}, chronic tennis elbow²¹, and post-operative pain control for lower limb lengthening correction^{16, 42}, among others. These observations suggest an anti-nociceptive action for BTX-A, which seems to be independent of its paralytic effect based on neuromuscular junction blockade. Only a few anecdotal reports exist that describe the positive effect of BTX-A on pain management in women with subpectoral tissue expanders and breast implants.⁶³⁻⁶⁷

The use of BTX-A in myocutaneous flaps has been studied in animals. A previous study indicated that BTX-A can prevent myocutaneous flap contraction, thus stabilizing pedicled muscle flaps.⁶⁸ Using an experimental animal model, Chenwang et al. studied the effect of BTX-A in tissue expansion. It was found that BTX-A could eliminate isometric muscle contractions and significantly increase the speed of expansion of myocutaneous flaps.⁶⁹

1.4 Clinical Data to Date

Specific to the present application, our research team performed a systematic review of the literature, to identify existing data on the use of BTX-A with subpectoral tissue expanders and implants.²⁴ We identified a retrospective study published by Layeeque et al.²⁵ in *Annals of Surgery* in 2004, on the effect of BTX-A use on pain during tissue expansion. In this retrospective study, pain was scored using a visual analog scale ranging from 0 to 10, with higher scores indicating increased pain. Keeping in mind the biases inherent to retrospective studies, the authors did report a significant reduction in postoperative pain scores during the initial tissue expansion with the use of BTX-A (mean \pm standard deviation of 1.95 ± 1.88 versus 5.61 ± 2.77 in the BTX-A group compared with the non-BTX-A group, respectively). These data support our hypothesis that BTX-A has the potential to significantly improve pain morbidity associated with tissue expansion. Case reports and expert opinions comprised the remaining available data describing the positive effect of BTX-A on pain management in women with subpectoral tissue expanders and breast implants.^{63-67, 70} However, it is difficult to draw any reliable conclusions from these reports as they all lack comparison with control groups. Thus, our systematic review has helped to identify a lack of prospective data on the efficacy of BTX-A in tissue expander breast reconstruction. Furthermore, no preliminary data was found on the impact of acellular dermal matrix (ADM) use on pain during tissue expansion. The preceding citations and critical analysis demonstrate the need for a prospective study on the efficacy of BTX-A use in reducing pain in women undergoing subpectoral tissue expander placement to guide an evidence-based practice, and this is precisely the focus of our specific aim. Since 2008, BTX-A has been routinely used at Mayo Clinic to alleviate pain and relieve muscle spasm associated with tissue expansion in women undergoing two-stage prosthetic breast reconstruction with and without the use of ADM. A preliminary analysis of our data supports the findings previously reported by Layeeque et al. Although this unpublished pilot data was not adequately powered and was lacking in the collection of possible confounding variables, the reduction in pain intensity scores was higher in women who underwent subpectoral tissue expander placement without the use of ADM. In this proposal, we will address these limitations in order to more rigorously evaluate pain and physical well-being outcomes in this larger, hypothesis-driven study.

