7.1 Sample Size Determination

The *primary study endpoint* is to determine the efficacy of a single intra-operative injection of BTX-A in the pectoralis major muscle on pain and physical well-being in women undergoing tissue expansions following mastectomy and immediate tissue expander breast reconstruction.

Secondary study endpoints include:

- 1) The initial percent volume expansion (defined as initial intraoperative fill volume divided by manufacturer recommended total tissue expander volume);
- 2) The rate of tissue expansion between the BTX-A groups and the placebo and control groups, with or without the use of ADM;
- 3) Rate of reconstructive failure (tissue expander removal for reasons such as infection or uncontrolled pain).

The *primary safety endpoints* of this study is the incidence of side effects attributable to the injection of BTX-A at doses of 100 units and 200 units, in women undergoing immediate post-mastectomy breast reconstruction with tissue expander(s).

Power and Sample Size: The only available preliminary data for the effect of BTX-A use on pain during initial tissue expansion were obtained from Layeeque et al, *Annals of Surgery* 2004. In this retrospective study, pain was scored using a visual analog scale ranging from 0 to 10, with higher scores indicating increased pain. Layeeque et al reported a mean \pm standard deviation (SD) pain score during initial tissue expansion of 1.95 ± 1.88 for the BTX-A group compared with 5.61 ± 2.77 for the non- BTX-A group.

Sample size estimates were obtained assuming 80% power and a significance level of 0.05 for a two-sample t-test to test the effects of BTX-A use on pain during initial tissue expansion. The table below (entitled Sample Size Estimates) summarizes the sample size needed in each group to achieve approximately 80% power. We calculated the sample sizes needed to detect a 50% decrease in the mean pain scores (assuming mean pain scores for the BTX-A and non-BTX-A groups of 2.0 and 4.0) and a 25% decrease in mean pain scores (assuming mean pain scores for the BTX-A and non-BTX-A groups of 3.0 and 4.0). Sample sizes were calculated assuming low, moderate, and high SDs of 2.0, 2.5, and 3.0, respectively. For example, if mean pain scores for the BTX-A and non-BTX-A groups

were 3.0 and 4.0, respectively, with a moderate SD of 2.5, 100 patients in each group, for a total of 200, would be required to detect this difference as statistically significant.

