In order to minimize cost while still maintaining scientific integrity, our goal is to accrue up to 134 patients in order to obtain 128 complete data sets (64 patients per study arm). If the accrual rate was slower than anticipated, we would extend the enrollment period and continue to accrue patients until sample size requirements were met. If the required number of enrolled subjects was not met for any reason, we would end the study and analyze the data using the same techniques. An appropriate cautionary statement would be added to the discussion section of any publication.

SAMPLE SIZE ESTIMATES

BTX-A	Mean Pain	SD	N per Group
No	4.0	2.0	17
Yes	2.0		
No	4.0		64
Yes	3.0		
No	4.0	2.5	26
Yes	2.0		
No	4.0		100
Yes	3.0		
No	4.0	3.0	37
Yes	2.0		
No	4.0		143
Yes	3.0		

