7.2 Statistical Methods**Descriptive Statistics:**

Demographic and medical characteristics will be analyzed for all enrolled subjects. Descriptive statistics will be calculated for all baseline variables. Univariate descriptive statistics and frequency distributions will be calculated, as appropriate for all variables. Baseline values for demographic, clinical, and outcome variables (primary and secondary) will be tabulated separately for the treatment groups. These analyses will help identify whether the randomization was successful in equalizing distributions of these prognostic variables across treatment groups or if confounding variables need to be included as covariates in sensitivity analyses. Putative prognostic variables that will be investigated through these descriptive analyses include variables such as age, body mass index, smoking status, diabetes mellitus, coronary artery disease, hypertension, clinical breast cancer stage, mastectomy weight, initial percent volume expansion (defined as initial intraoperative fill volume divided by manufacturer recommended total tissue expander volume), sentinel lymph node biopsy, axillary dissection, adjuvant therapy factors (e.g., previous and postoperative chemotherapy and radiation), operative time, ADM use.

Handling of Missing Data

Handling of missing data will be done in a number of ways including complete-case analysis and multiple imputations via nearest neighbor, mean value, last value, and zero value carried forward

approaches. Multiple approaches are used so that the sensitivity of results to alteration in multiple imputational assumptions may be assessed.

Primary Hypotheses:

- Pain scores will be at least 25% less, in those who received BTX-A, during the immediate post-operative period compared to those who received saline injections
- Pain scores will be at least 25% less, in those who received BTX-A, during the period of tissue expansion, compared to those who received saline injections
- Physical Well-Being scores during tissue expansion will be higher in those who received BTX-A compared to those who received saline injections

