There are two primary outcomes: pain intensity measured by the NPIS, and physical well-being using the BREAST-Q®. The primary analysis will be performed during the post-operative period and during the expansion phase. Outcome variables will be summarized with frequency counts and percentages or means, standard deviations, medians, and ranges, as appropriate. The mean, median, standard deviation, and range of each variable and its change from baseline, measured on a continuous scale, will be presented by treatment and visit. Frequency tables will be provided for categorical variables by treatment and visit. Any differences among the study groups will be evaluated using two-sample t, Wilcoxon rank sum, Pearson's chi-square, or Fisher's exact tests.

Secondary Hypotheses:

- 1) There will be no difference in the initial percent volume expansion between groups (defined as initial intraoperative fill volume divided by manufacturer recommended total tissue expander volume);
- 2) The rate of tissue expansion will be higher in the BTX-A groups compared to the placebo group, with or without the use of ADM;
- 3) There will be no difference in the rate of reconstructive failure (tissue expander removal for reasons such as infection or uncontrolled pain).

The volume of tissue expansion anticipated and the rate of tissue expansion between the BTX-A groups and the placebo and control groups will be calculated both as an absolute value as well as a percentage. It is hypothesized that the use of BTX-A may increase the rate of tissue expansion, which may lead to fewer postoperative tissue expansion visits. This will allow measurement of effect size between the intervention and the placebo groups. Two-sample t and Wilcoxon rank sum tests will be used for the secondary analyses.

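### The pilot hinted at a larger pain reduction without ADM, but no BTX-A effect by ADM use is pre-specified for pain or BREAST-Q

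*Combined protocol and SAP*

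**What the plan says.** **Signal.** Section 1.4 says of the pilot that "the reduction in pain intensity scores was higher in women who underwent subpectoral tissue expander placement without the use of ADM". It qualifies this at once: the pilot lacked power and did not collect possible confounders. It then says "In this proposal, we will address these limitations". Section 1.1 lists less pain among the possible benefits of ADM, and adds that prospective trials have not shown a benefit of ADM on postoperative pain.

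**Design.** Section 5.3 defines both arms, BTX-A and placebo, as with or without ADM. Allocation is by random numbers, and no stratification by ADM is stated. The surgeon does not know the allocation at injection.

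**Analysis.** For the primary outcomes, section 7.2 states "Any differences among the study groups will be evaluated using two-sample t, Wilcoxon rank sum" (with chi-square and Fisher tests for categorical data). Section 7.3 applies this to all randomised women. ADM enters section 7.2 in two places:
- It closes the list of putative prognostic variables ("operative time, ADM use"). Variables on that list may become covariates in sensitivity analyses if the baseline tables suggest a need.
- It is named in the secondary hypothesis on rate of expansion.

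**Sample size.** Section 7.1 works with one group difference for all women, and gives no expected share of women with ADM.

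**The concern.** The only hint in the documents that BTX-A may act differently in different women concerns ADM and pain. Yet the plan names ADM for a secondary endpoint and gives no treatment effect by ADM for pain or physical well-being.

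The covariate provision does not fill this gap. It depends on what the baseline tables show, and adjusting for a prognostic variable still yields a single common treatment effect. With ADM perfectly balanced between arms the provision would not be used, although the effect could still differ by ADM.

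At stake is interpretation. If the effect does differ, the pooled estimate is an average that moves with how often surgeons use ADM. A null result might hide a benefit in women without ADM, and a positive one might be carried over to women with ADM who gain less. Any split made after the data are seen would be post hoc.

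**Working it through.** **1. Reproduce the plan's figure.** Inputs from section 7.1:
- test: "assuming 80% power and a significance level of 0.05 for a two-sample t-test"; sidedness is not stated, and two-sided is taken here
- effect: means of 4.0 and 3.0, a difference of 1.0
- SD: the lowest of "low, moderate, and high SDs of 2.0, 2.5, and 3.0, respectively"
- target: "accrue up to 134 patients in order to obtain 128 complete data sets (64 patients per study arm")

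The two-sided t-test at standardised difference 1.0/2.0 = 0.5 needs 63.77, so 64 per arm. Power at 64 is 80.2%. The stated size is correct for an average difference of 1.0 and SD 2.0.

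**2. Pooled effect if the effect differs by ADM.** Let p be the share of women with ADM, equal in both arms. Then

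pooled difference = (1 − p) × effect without ADM + p × effect with ADM.

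The documents give neither p nor either effect, so every row below is an assumption. Power is for the two-sided t-test, 64 per arm, within-arm SD 2.0.

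| Effect without ADM | Effect with ADM | p | Pooled difference | Power |
|---|---|---|---|---|
| 1.0 | 0.5 | 25% | 0.875 | 69% |
| 1.0 | 0.5 | 50% | 0.75 | 56% |
| 1.0 | 0.5 | 75% | 0.625 | 42% |
| 1.0 | 0 | 50% | 0.50 | 29% |
| 1.5 | 0.5 | 50% | 1.0 | 80% |
| 2.0 | 0.5 | 50% | 1.25 | 94% |

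The first four rows take the planning difference of 1.0 as the effect in women without ADM, so power can only fall. The last two start from a larger effect in those women; 2.0 is the plan's own 50% scenario (4.0 versus 2.0). All six fit the pilot sentence equally well.

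**3. What an analysis by ADM could show at N = 128.** With p = 50% there are 32 women per arm in each ADM group.
- SE of the treatment difference in one group = 2.0 × √(2/32) = 0.50; 95% half-width = 1.96 × 0.50 = 0.98 points.
- SE of the interaction = 2.0 × √(2/32 + 2/32) = 0.707; 95% half-width = 1.96 × 0.707 = 1.39 points.
- Power of the interaction test (normal approximation) is 29% for a gap of 1.0 point and 11% for a gap of 0.5. A gap of about (1.96 + 0.84) × 0.707 = 1.98 points is needed for 80%.

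**4. Definition of ADM use.** In the section 3.1 table, bilateral cases are 123 + 111 + 107 = 341 of 221 + 185 + 177 = 583, or 58%. A yes/no variable per woman therefore needs a rule for bilateral cases, and the plan has none.

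**The case against.** The strongest reply is that nothing in the plan is wrong. The aim in section 2 is the effect of BTX-A in women with subpectoral expanders, the arms openly allow ADM, and the randomised comparison of all women is unbiased with correct type I error. Any average effect depends on case mix. All of this stands.

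Four stronger readings are tempting, and the documents do not support them:
- **That the pilot established effect modification.** The sponsor itself calls it underpowered and lacking confounder data, and gives no sizes. Section 1.1 treats pain relief from ADM as possible only; even if real, it would make ADM prognostic and would not show that BTX-A works less well with it.
- **That the sponsor promised an ADM analysis.** The limitations that section 1.4 undertakes to address are power and missing confounders. Randomisation, a sample size calculation and a list of prognostic variables respond to those.
- **That the trial is underpowered because of ADM.** Section 7.1 describes its scenario as "a 25% decrease in mean pain scores (assuming mean pain scores for the BTX-A and non-BTX-A groups of 3.0 and 4.0"), a difference between whole groups. Taking 1.0 as the effect without ADM is a choice; with 1.5 and 0.5 at 50% use, power is the planned 80%.
- **That ADM is known to be chosen during surgery.** The documents do not say when. The case for comparing arms within ADM groups rests on masking: the surgeon does not know the allocation (section 5.3), and section 1.5 puts the paralytic action at about 7 to 10 days, so the choice of ADM should not depend on treatment.

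It is also fair to say that subgroup estimates this imprecise could not attribute a null result to ADM. That limits the fix to estimation. It does not remove the case for it, because the alternative is the same imprecise split made after the results are known.

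**Conclusion.** The point holds as a gap in pre-specification. The plan records a possible difference in effect by ADM, admits women with and without ADM to both arms, and sets out no BTX-A effect by ADM for pain or BREAST-Q. The primary test is neither biased nor invalid.

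The effect on power cannot be fixed from the documents. If the effect is halved with ADM and 1.0 without, power runs from 69% to 42% as ADM use goes from 25% to 75%; if the average is still 1.0 there is no loss. These figures assume SD 2.0, 64 complete cases per arm and equal ADM use in both arms. The change is worthwhile because it is cheap and examines the sponsor's own signal in randomised data.

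**What to change.** In section 7.2:
- Define ADM use per woman, with a rule for bilateral cases (for example, ADM on either side).
- Include ADM use as a factor in the analysis of pain and BREAST-Q whether or not it is imbalanced. For the t-test this means a linear model with treatment and ADM, which replaces a covariate choice triggered by baseline imbalance.
- As a named supportive analysis for both primary outcomes, report the BTX-A minus placebo difference with 95% CI in women with and without ADM, and the treatment-by-ADM term with its CI.
- State that this is estimation, outside the primary tests.

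The cost is SAP wording and one further model per outcome, on a variable already listed. No extra patients or visits are needed. The drawback is the low precision shown above. The change does not restore power if the pooled effect is diluted, and a wide interval for the interaction must not be read as evidence that the effect is the same.
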